### 6.5.2 Cycle 1, Day -15 (C1D-15)

All patients in the Surgical study cohort will undergo **craniotomy and tumor re-resection** at least 1 week after and within **2 weeks** from first dose of ipilimumab and nivolumab. The following study procedures will be performed:

- Adverse event assessment
- Concomitant medication collection
- Symptom-directed physical exam as clinically indicated by the investigator or qualified designee at all mid-cycle visits
- Vital signs: When scheduled at the same visit as other procedures, vital signs should be measured prior to clinical laboratory assessments or research blood sample collection.
  - Weight (can be taken within 3 days of scheduled study drug administration)
  - Temperature, resting blood pressure, pulse and respiration rate.
- Serum chemistry: sodium, potassium, chloride, bicarbonate, calcium, magnesium, phosphorous, glucose, albumin, creatinine, blood urea nitrogen (BUN), uric acid, ALT, AST, total bilirubin, direct and/or indirect bilirubin, alkaline phosphatase (ALP), lactate dehydrogenase (LDH), amylase, and lipase.
- Hematology: WBC count, 3-cell differential (ANC, monocyte count, lymphocyte count), hemoglobin, hematocrit, and platelet count
- Urinalysis: glucose, blood, pH, specific gravity, ketones, and urine protein
- During the surgery, a tumor specimen will be collected for research studies:
  - Assessment of tumor tissue biomarkers including mutation burden, neoantigen load, immune marker expression [e.g. PD-L1, lymphocyte activation gene 3 (LAG3), indoleamine-2,3dioxygenase (IDO) and T-cell immunoglobulin and mucin domain 3 (TIM3)], and PD-1+ tumor infiltrating lymphocytes (TILs).
- Research blood samples. All subjects will have the below research blood samples collected at time of surgery. Note: Research blood samples will be taken at 3 time points: **Cycle 1, Day -29 (pre-dose)**, **Cycle 1, Day -15 (surgery)** and **Cycle 1, Day 15** (end of week 6). The blood on the surgical date may be taken before or after the surgical procedure.

A total of 40 mL (four 10 mL purple top EDTA tubes) of whole blood will be drawn and immediately sent to the below sites:

- One (1) 10 mL tube will be sent to the Center for Biospecimen Research and Development (CBRD) at NYU School of Medicine (NYU SoM) for acquisition of whole blood, buffy coat, and plasma samples.
- Three (3) 10 mL tubes will be sent to the Immune Monitoring Core (IMC) at NYU SoM and immediately processed for isolation of PBMCs.

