**Objectives:**

*Primary*

- **Main Study Cohort:** To estimate the overall survival at 1 year (1-yr OS) of adults with newly diagnosed, *MGMT* unmethylated GBM administered nivolumab, ipilimumab and hypofractionated RT.
- **Surgical Study Cohort:** To assess Safety, Feasibility, and Tolerability of neoadjuvant ipilimumab and nivolumab (prior to tumor re-resection), and estimate rate of T-cell pathway induction.

*Secondary*

- **Main Study Cohort**
  - Assess safety and tolerability
  - Estimate additional measures of efficacy, including 2-year OS, median OS, median PFS, radiographic response rate, and median duration of response.
- **Surgical Study Cohort**
  - Estimate efficacy measures including 1-yr OS, 2-year OS, median OS, median PFS, radiographic response rate, and median duration of response.

*Exploratory*

- Assess association of 1-yr OS with: tumor tissue biomarkers including mutation burden, neoantigen load, immune marker expression [e.g. PD-L1, lymphocyte activation gene 3 (LAG3), indoleamine-2,3-dioxygenase (IDO) and T-cell immunoglobulin and mucin domain 3 (TIM3)], and PD-1+ tumor infiltrating lymphocytes (TILs).
- Assess association of 1-yr OS with baseline and change at 6 weeks in levels of circulating biomarkers, including: regulatory T cells ( $T_{reg}$ ); myeloid-derived suppressor cells (MDSC); and immune cell populations as profiled by high-parameter flow cytometry that simultaneously quantifies expression of proteins related to checkpoint inhibitors (PD1, CTLA4, TIM3, TIGIT, 41BB, CD150, LAG3, BTLA), differentiation status (CD45RA, CCR7, CD57, CD95, CD127), and other traits (CD25, IL12R, CXCR3, CXCR6).
- Evaluate effect of study regimen on total lymphocyte counts (TLC) and CD4 counts at fixed timepoints for up to 1 year compared to baseline.
- Explore whether sodium MRI, a non-invasive surrogate measure of cell death in tissue, can differentiate between treatment-related cell death/necrosis ("pseudoprogression") versus tumor progression and serve as a potential non-invasive pharmacodynamic biomarker.

CONFIDENTIAL

This material is the property of the NYU School of Medicine. Do not disclose or use except as authorized in writing by the study sponsor

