#### **Surgical Study Cohort:**

- The primary objective is safety, feasibility and tolerability

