## **4 Subject Selection**

### **4.1 Inclusion Criteria**

1. Male or female subjects aged  $\geq 18$  years.
2. Histopathological evidence of glioblastoma or gliosarcoma, WHO grade IV.
3. Tumor *MGMT* promoter DNA not methylated (i.e., unmethylated) by central testing.

CONFIDENTIAL

This material is the property of the NYU School of Medicine. Do not disclose or use except as authorized in writing by the study sponsor

4. There will be two study cohorts:
  - **Main Study Cohort:** Maximal tumor diameter of 6.6 cm or less. Patients with multifocal tumors are allowed if the sum of the maximal tumor diameters does not exceed 6.6 cm. Note, the maximal tumor diameter for the first 3 subjects enrolled will be 5 cm.
  - **Surgical Study Cohort:** Patients who received tumor biopsy or subtotal tumor resection and are amenable to a second tumor resection with expected post-operative tumor diameter of  $\leq 6$  cm (PTV of  $\leq 150$  cm $^3$ )
5. Subjects must not have received any prior standard or investigational anti-tumor therapy other than surgery and must not intend to receive any standard or investigational anti-tumor therapy other than the study regimen.
6. Karnofsky performance status (Appendix 2) of  $\geq 60$ .
7. Availability of a paraffin-embedded or frozen tumor-tissue block with a minimum of 1 cm $^2$  of tumor surface area, or 20 unstained slides from the glioblastoma tissue specimen if a tumor block cannot be submitted. . For Surgical Study Cohort: availability of pre- and post-operative tumor tissue is required.
8. Subjects must start study agent within 6 weeks from the first diagnostic surgery for glioblastoma.
9. Begin of Study Treatment:
  - An interval of at least 2 weeks for surgical resection and 1 week for stereotactic biopsy from the start of study treatment. **Main Study Cohort:** Subjects must start study agents no sooner than 2 weeks from last surgical resection and 1 week from stereotactic biopsy.
  - **Surgical Study Cohort:** Subjects must receive 1st dose of study agents 2 weeks prior to tumor re-resection and must resume study agents no sooner than 2 weeks from date of tumor re-resection.
10. A contrast-enhanced MRI must be obtained within 21 days of the first dose of study treatment.
11. Adequate hematologic, hepatic, and renal function defined by
  - a. White blood cell count  $\geq 2.0 \times 10^9/L$
  - b. Absolute neutrophil count  $\geq 1.5 \times 10^9/L$
  - c. Platelet count  $\geq 100 \times 10^9/L$

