### **4.5 Registration Procedures**

#### **4.5.1 General Guidelines**

Each patient must sign and date an informed consent form before undergoing any study specific procedure unless a procedure is being performed as part of the patient's standard of care.

Enrollment in the study requires that all inclusion and exclusion criteria have been met. Enrollment occurs upon confirmation of registration from the NYU School of Medicine PCC Clinical Trials Office (CTO). The following materials must be submitted to the Research Coordinator for registration:

1. Complete signed and dated informed consent form
2. Complete signed and dated informed consent checklist
3. Complete signed and dated eligibility checklist
4. All supporting documentation verifying each criterion has been met

Registration will occur within 48 hours of research coordinators' receipt of all the above documents. A written confirmation of enrollment including a unique study identification number assigned by the research coordinator will be distributed to the study team upon registration.

Pretreatment evaluation will therefore be dictated by standard clinical practice. Eligible patients will be entered into the study by the study coordinator.

All patients will be required to sign a written informed consent prior to being registered on this study. Any patient not registered to the study before treatment begins will be considered ineligible and registration will be denied. Every effort will be made to answer questions raised by patients and their families or

CONFIDENTIAL

This material is the property of the NYU School of Medicine. Do not disclose or use except as authorized in writing by the study sponsor

advocates regarding the protocol and alternative therapies prior to asking a patient to sign the consent form.

Once eligibility is verified, a unique patient study number will be issued within 24 hours of receiving all required registration material. The patient will not be identified by name. This is the point, at which, the patient is considered on the study. Subjects must not start any protocol study specific procedures, unless part of standard of care prior to registration

Issues that would cause treatment delays should be discussed with the Overall Principal Investigator.

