### 6.11.3 Fresh Surgical Tumor Specimen (if available)

After informed consent, if subjects undergo tumor resections or biopsies prior to treatment initiation, during the study period, or after progression on study drug, a small amount fresh surgical specimen (less than 0.5 cm^2, approximately equivalent to amount required for a stereotactic needle biopsy) will be collected for short-term (6-8 days) organotypic tumor spheroid culture and for dissociation into single cell suspensions for flow-cytometry-based immunoprofiling. Fresh tumor specimen will only be collected after verifying that enough tumor sample for diagnosis and clinical care is available. All tumor material collected will be used for these specific purposes only. Tumor sample will be collected in medium (DMEM) in a sterile cryotube and immediately transported on ice to [name] laboratory at NYU Langone for immediate processing.

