### 2. Tumor Tissue RNA-Seq

CONFIDENTIAL

This material is the property of the NYU School of Medicine. Do not disclose or use except as authorized in writing by the study sponsor

**Objective:** To use tumor tissue RNA-Seq data to evaluate the fraction of predicted mutation-associated neoantigens derived from somatic whole-exome sequencing data that is expressed and assess the association of PFS6 and number of expressed mutation-associated neoantigens.

**Expression of predicted mutation-associated neoantigens:** We will estimate the proportion of predicted mutation-associated neoantigens that are expressed by RNA-Seq and compare the expressed predicted mutation-associated neoantigen load between tumors that achieve PFS6 and those that do not. Total RNA will be extracted from FFPE tumor tissue using RNA extraction kits, treated to remove genomic DNA, quantified, and analyzed for integrity. RNA-Seq libraries will be prepared using standard protocols to purify poly-adenylated mRNA, generate double-stranded cDNA and ligate adapters and then submitted for next-generation sequencing

**Clonality of mutation-associated expressed neoantigens:** If enough tumor tissue is available to assess distinct regions of an individual tumor, we will perform RNA-Seq analyses on different regions of each tumor to assess the clonality of expressed neoantigens.

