### 4. Tumor immunoprofiling using Patient-Derived Organotypic Tumor Spheroid (PDOTS) Culture and Flow Cytometry

CONFIDENTIAL

This material is the property of the NYU School of Medicine. Do not disclose or use except as authorized in writing by the study sponsor

**Objectives:** Fresh surgical tumor specimens, if available, will be used for:

**A)** Flow cytometry-based immunoprofiling of dissociated, single cell suspensions.

**B)** Characterization of baseline cytokine profiles in patient-derived organotypic tumor spheroid (PDOTS) short term culture system and change in cytokine profiles after immune checkpoint blockade.

**A) Flow cytometry-based immunoprofiling of dissociated, single cell suspensions:** A small portion of freshly resected tumor tissue (0.5 cm^2, equivalent to 4 stereotactic needle biopsy specimens) placed in a sterile cryotube in media (DMEM) will be taken immediately on ice to [name] lab at NYULH. In the lab, half the tumor specimen will be immediately processed into single cell suspensions for flow cytometry-based immunoprofiling in the Immune Core at NYU. The other half of the specimen will be used for objective B below.

**B) Characterization of baseline cytokine profiles in patient-derived organotypic tumor spheroid (PDOTS) short term culture system and change in cytokine profiles after immune checkpoint blockade:** Half of the fresh surgical tumor specimen will be used immediately for short-term (6-8 days) *ex vivo* PDOTS culture. PDOTS cultures isolated from human tumors retain autologous lymphoid and myeloid cell populations, thus incorporating features of the tumor microenvironment, in short-term 3-dimensional microfluidic culture. The PDOTS microfluidic culture system was developed by [name], PhD, and these experiments will be performed in his lab at NYULH. Cell suspensions from the fresh surgical specimens will be prepared and loaded into 3D microfluidic devices. After 3 days, PDOTS culture fresh medium +/- immune checkpoint blockers (anti-PD-L1 and anti-CTLA4 antibodies) will be added. After further 3-5 days of PDOTS culture, conditioned medium will be obtained for baseline and post-immune checkpoint blockade cytokine and chemokine profiling using Luminex arrays.

All fresh surgical tumor specimen collected will be used for these specific purposes only. No cell lines will be generated and true genetic testing will not be performed.

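### The surgical cohort is sized on T-cell pathway induction, but no assay for it is assigned to the re-resection tissue, and the entry and population rules around that tissue do not fit

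*Combined protocol and SAP*

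**What the plan says.** **Status of the outcome.** The synopsis objectives give the surgical cohort a primary aim of safety, feasibility and tolerability, and also to "estimate rate of T-cell pathway induction". Section 3.2 says only "The primary objective is safety, feasibility and tolerability", and Section 2.2 agrees with Section 3.2. Section 7.2.3 introduces the design as one for estimating overall survival, then states hypotheses on induction (33% versus 64%, 16 patients). The synopsis sample-size paragraph gives the same two rates but attaches the power to 1-year OS.

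**Tissue and assays.** Section 6.5.2 collects a research tumor specimen at C1D-15 for "Assessment of tumor tissue biomarkers including mutation burden, neoantigen load, immune marker expression" and PD-1+ infiltrating lymphocytes. In the Appendix 2 schedule, the only tumor-tissue mark at C1D-15 carries footnote 36: fresh tissue for spheroid culture and flow cytometry. Of that fresh tissue, Section 6.11.3 says "All tumor material collected will be used for these specific purposes only", and Appendix 7 adds "No cell lines will be generated and true genetic testing will not be performed". The RNA-Seq section of Appendix 7 aims to "assess the association of PFS6 and number of expressed mutation-associated neoantigens".

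**Entry and population.** For the surgical cohort, inclusion criterion 7 says "availability of pre- and post-operative tumor tissue is required". The registration packet in Section 4.5.1 must hold "All supporting documentation verifying each criterion has been met". Section 7.3.4 defines the cohort's safety and efficacy population as patients with at least one dose who also undergo re-resection.

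**The concern.** An outcome that fixes a sample size needs a specimen, an assay, a reference and a rule for calling a patient positive. Here only the two rates are given. If the signature and cut-off are chosen after the data are in hand, the cohort's one numerical hypothesis loses its protection against selective definition.

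Two further rules bear on the same tissue. One asks at entry for tissue that has not yet been taken. The other removes dosed patients who do not reach surgery, and those patients carry most of the information on whether dosing before surgery is feasible and safe.

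**Working it through.** **1. The plan's own figure.** Inputs: N = 16, null rate 0.33, alternative 0.64 (Section 7.2.3). Section 7.1 takes the rates from a cited trial in recurrent disease: 5/15 = 33.3% and 9/14 = 64.3% of tumors. Exact binomial:
- One-sided 0.05, success if X ≥ 9: P(X ≥ 9 | 16, 0.33) = 0.047; P(X ≥ 9 | 16, 0.64) = 0.819. This reproduces the stated 80%.
- Two-sided 0.05 as labeled (upper tail at most 0.025), success if X ≥ 10: P(X ≥ 10 | 16, 0.33) = 0.015; power 0.657.

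So N = 16 is an induction calculation and reproduces as a one-sided test. The two-sided label is a separate matter.

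**2. Where could induction be measured?** Each tissue route in turn:
- *Section 6.5.2:* C1D-15 specimen; mutation burden, neoantigen load, immune markers, PD-1+ lymphocytes. Induction not named.
- *Appendix 2, archival tissue row:* marked at screening only.
- *Appendix 2, surgical specimen row, footnote 36:* spheroid culture and flow cytometry.
- *Section 6.11.4:* frozen or FFPE tissue from a resection after treatment starts, if the patient consents. The re-resection follows the first dose, so read literally this makes its tissue optional.
- *Appendix 7, exome sequencing and immunohistochemistry:* each has a step for post-treatment tissue; neither mentions induction.
- *Appendix 7, RNA-Seq:* neoantigen expression against PFS6; no post-treatment step.
- *Section 7.2.4:* RNA-Seq immune-cell levels compared by 1-year survival, labeled exploratory.

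No route assigns an induction assay, and none gives a reference sample or threshold.

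**3. Can criterion 7 be met at registration?** Section 4.5.1 requires registration before treatment. Section 6.1.3 puts the first doses at C1D-29 and re-resection at C1D-15: 29 − 15 = 14 days later. Section 6.5.2 allows surgery from 1 week after the first dose. The tissue therefore first exists 7 to 14 days after the latest point at which the criterion can be documented.

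**4. Who is counted?**
- Dosed, re-resected, adequate tissue: in the Section 7.3.4 population.
- Dosed, re-resected, inadequate tissue: also in it, since there is no tissue condition. How the patient counts in the induction rate is not stated.
- Dosed, never re-resected: outside it.

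**5. Why the counting rule matters.** N = 16 has no allowance for unusable tissue, and the documents give no expected rate, so these values are assumptions. With only evaluable patients analyzed and the exact one-sided cut-off re-derived:
- 15 evaluable (≥ 9): power 72.8%
- 14 (≥ 9): 61.0%
- 13 (≥ 8): 68.9%
- 12 (≥ 8): 55.4%

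The sequence is uneven because the cut-off is a whole number. If all 16 stay in, the cut-off stays at 9 and unusable tissue counts as not induced, the alternative becomes 0.64 × 0.9 = 0.576 with 90% evaluable (power 64.5%), or 0.64 × 0.8 = 0.512 with 80% evaluable (power 44.0%).

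**The case against.** The other side has real points.
- Only the synopsis calls induction primary. That stands, so the passages need reconciling. Whatever its label, it is still the quantity that sets N.
- The list in Section 6.5.2 is open-ended, tissue is collected at C1D-15, and an RNA-Seq platform is planned. This also stands. A reader might infer that induction cannot be measured at all; the documents do not support that. The means are foreseen, but no section connects them to the outcome.
- A reader might take the limit in Section 6.11.3 to bar all re-resection tissue from other assays. It sits in a section on a fresh aliquot under 0.5 cm², and Section 6.5.2 gives C1D-15 tissue other uses, so it is naturally read as covering the aliquot alone.
- Criterion 7 sits beside other forward-looking criteria, such as expected post-operative diameter, and can be read as a commitment to provide tissue. That is probably the intent, but the text asks for availability.
- A reader might infer that patients with inadequate tissue would later be dropped as ineligible, inflating feasibility and the induction rate. No section contains such a rule, and Section 7.3.4 keeps every re-resected patient.
- Section 7.3.3 keeps all dosed patients in the study-wide safety analysis. For safety, then, Section 7.3.4 conflicts with another section and does not by itself remove these patients from all safety reporting. Section 7.3.3 does not address feasibility.

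**Conclusion.** The point holds in this form. The cohort is sized only on T-cell pathway induction, the documents disagree on the status of that outcome, and no assay, reference or cut-off for it is assigned to the C1D-15 tissue. This affects all 16 planned patients. Two linked defects also hold: criterion 7, read literally, cannot be documented at registration, and Section 7.3.4 omits dosed patients who are not re-resected from a cohort meant to assess safety and feasibility.

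The gap itself follows from the text and needs no assumption. The power figures for fewer evaluable samples rest on assumed evaluability rates; they show only that the counting rule matters. No bias in the induction rate can be quantified from the documents. Nor do they show whether the 33% and 64% benchmarks were scored on paired samples: Section 7.1 reports two groups of tumors.

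**What to change.** 1. In Section 6.5.2, the Appendix 2 specimen row and Appendix 7, state that frozen or FFPE tissue from the C1D-15 re-resection will undergo RNA-Seq to score T-cell/interferon pathway induction. Fix the signature, the reference sample (chosen to match how the 33% and 64% benchmarks were scored) and the cut-off before outcome data are seen. Make this collection mandatory for the surgical cohort, outside the optional consent of Section 6.11.4.
2. Give induction one status across the synopsis objectives, the synopsis sample-size paragraph and Sections 2.2, 3.2 and 7.2.3, and remove the survival wording from the induction design.
3. In inclusion criterion 7, replace post-operative tissue availability with diagnostic tissue available and agreement to tissue collection at re-resection.
4. Amend Section 7.3.4 so that all dosed patients count for safety and feasibility. Report those not re-resected or without usable tissue as feasibility failures, and state how they count in the induction rate.

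The cost is protocol wording plus RNA-Seq on up to 16 specimens from surgery already planned, with no extra biopsy or visit. The feasibility rate may look less favorable once every dosed patient is counted.

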### 6.5.3 Cycle 1, Day 1 (C1D1)

CONFIDENTIAL

This material is the property of the NYU School of Medicine. Do not disclose or use except as authorized in writing by the study sponsor

Two weeks (+/- 3 days) after craniotomy and tumor re-resection, the subject will return for second dose of nivolumab 3 mg/kg IV. The following study procedures will be performed:

- Adverse event assessment
- Concomitant medication collection
- Complete physical exam, including neurological exam, and KPS assessment
- Vital signs: When scheduled at the same visit as other procedures, vital signs should be measured prior to clinical laboratory assessments or research blood sample collection.
  - Weight (can be taken within 3 days of scheduled study drug administration)
  - Temperature, resting blood pressure, pulse and respiration rate.
- Serum chemistry: sodium, potassium, chloride, bicarbonate, calcium, magnesium, phosphorous, glucose, albumin, creatinine, blood urea nitrogen (BUN), uric acid, ALT, AST, total bilirubin, direct and/or indirect bilirubin, alkaline phosphatase (ALP), lactate dehydrogenase (LDH), amylase, and lipase.
- Hematology: WBC count, 3-cell differential (ANC, monocyte count, lymphocyte count), hemoglobin, hematocrit, and platelet count
- Urinalysis: glucose, blood, pH, specific gravity, ketones, and urine protein

